### 3.7.3 *Retreatment Criteria (Stage 1 and Stage 2)*

From Week 12 onwards (Stages 1 and 2), need for retreatment will be assessed at each visit. All subjects willing to continue in the study will be offered to receive Dysport (under an open-label design).

Retreatment with Dysport will only be initiated if all of the following criteria are fulfilled (retreatment criteria):

- At least 12 weeks have elapsed since the last treatment received.
- Based on investigator's judgement, this is in the best interest of the subject.
- Subject is willing to be retreated.
- The subject has not experienced any unacceptable AE as judged by the investigator.
- Negative urine pregnancy test.
- Negative drug screen test for illicit drugs.

Details on dose administration for Stage 1 are provided in Sections [3.7.2.1](#) and for Stage 2 in Section [3.7.2.2](#).

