### 4.1 Inclusion Criteria

All subjects must fulfil all the following criteria to be included in the study:

- (1a) Female subjects aged 18 years or above.
- (2) Willing to provide a written informed consent prior to any study related procedures.
- (3) *Criterion 3 is removed by protocol amendment.*
- (4) Are premenopausal, as evidenced by a serum follicle stimulating hormone (FSH) level of <35 mIU/mL as assessed at the Screening Visit.
- (5) Have a negative pregnancy test at screening.
- (6) Willing to practice a highly effective form of contraception method at the beginning of the study, for the duration of the study and for a minimum of 12 weeks following last administration of study drug. Highly effective methods of contraception are defined as methods of birth control which result in a low failure rate (i.e. less than 1% per year) when used consistently and correctly such as implants, injectables, combined oral contraceptives, intrauterine devices, or vasectomised partner. The double barrier method (condom and spermicide) may be considered an acceptable form of birth control if determined appropriate for the subject by the investigator.
- (7) Have vulvodynia with provoked vestibular pain for at least 6 months and for no more than 15 years.
- (8a) Have provoked pain at the posterior vestibule on a Q-tip test, with pain at positions 5, 6 and 7 o'clock (must be bilateral pain) at the Screening Visit.
- (9a) Are able to tolerate the smallest dilator size (diameter 0.5 inches) at the Screening Visit, i.e. agree to the next successive dilator size to be tested for pain response (i.e. the two smallest sized dilators (#1 and 2) are to be tested).
- (10a) Pain score  $\geq 5$  on an 11-point NRS for the DMTS at the Baseline Visit.
- (11a) Willing to abstain from sex therapy (defined as a therapy primarily focused on the management of vulvar pain) for the duration of screening and up to at least Week 6 of the first treatment cycle.
- (12b) In Stage 1, Cohorts 1, 2, 3, 5, 7, 9 and 11 will include subjects with secondary vulvodynia (i.e. having a past history of pain-free intercourse or insertion of any object >1 cm diameter). In Stage 1, Cohorts 4, 6, 8, 10 and 12 will include subjects with primary vulvodynia (having life-long provoked vestibular pain). In Stage 2, subjects with either primary or secondary vulvodynia may be enrolled as approved by the DRC.

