- Is likely to require treatment during the study with drugs that are not permitted by the study protocol.

(17) Any mental condition rendering the subject unable to understand the nature, scope and possible consequences of the study, and/or evidence of an uncooperative attitude, as judged by the investigator.

(18) Abnormal baseline findings, any other medical condition(s) or laboratory findings that, in the opinion of the investigator, might jeopardise the subject's safety or compromise compliance with the objectives and/or procedures of this protocol or preclude the administration of BTX.

(19) Female subject who is pregnant or planning to become pregnant during the study or, is currently lactating (breastfeeding).

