- a Day 1 should be done on the same day as last visit of previous cycle. During Stage 1, Day 1 can be delayed until the DRC has confirmed the dose for the next cohort.
- b From Week 12 onwards, if no retreatment is required, the subject will attend Additional Visits every 6 weeks until retreatment is required, or EOS is reached. When subject is eligible and all retreatment criteria all are fulfilled at any visit, the subject will complete the assessments planned at this visit and will enter Day 1 of the next Cycle on the same day and once the DRC has confirmed moving to next cohort for Stage 1.
- c Not to be performed if already done on the same day. AEs are assessed on a continual basis from signing of the ICF.
- d To be performed only if Day 1 is not on the same day as the last visit of previous cycle and the assessment was performed more than 2 weeks prior to Day 1.
- e To be assessed 2 weeks prior and 1 week prior to the next planned visit, and at the visit.

Study Procedures and Assessments	Open-Label Treatment Period Cycles 2 to 4						EOS / EWD
	V9, V13, V17	V10, V14, V18	V11, V15, V19	V12, V16, V20	Additional Visits [b]		
Visit Day/Week No.	Day 1 [a]	Week 2 (Day 15)	Week 6 (Day 43)	Week 12 [b] (Day 85)	Week 18 (Day 127)	Week 24 (Day 169)	Week 48 from Cycle 1 Day 1 (Day 337 from Cycle 1 Day 1) or Early withdrawal
Type of visit	Clinic	Telephone	Clinic	Clinic	Clinic	Clinic	Clinic
Visit Window		±3 days	±5 days	+14 days	±14 days	±14 days	±14 days

f To be recorded daily from 2 weeks prior to the next planned visit. Subjects need to record daily if they had intercourse, the number of intercourse instances, corresponding pain during each intercourse instance on an 11-point NRS and details of pain rescue medication if taken to prevent or treat vestibular pain.

g Performed after all the other procedures and assessments. Subjects to remain at the clinic for at least 30 minutes after the study drug administration.

h No assessment for retreatment if the visit occurs >36 weeks from Cycle 1 Day 1.

i To be assessed only in Cycle 2 (i.e. the first cycle of the open-label treatment period).

j To be assessed 1 week prior to the next planned visit and at the visit.

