## 5.2 Study Visits

For the purpose of study visits and procedures, the duration of 1 month=4 weeks=28 days. For assessments done at the Screening Visit, but not repeated at the Baseline Visit, the Screening values will be considered as Baseline.

Subjects are required to remain at the clinic for the required duration of study assessments and for at least 30 minutes after study drug administration.

The priority order for performing the assessments is discussed in Section 6.6.

If the COVID-19 pandemic prevents subjects from coming to the site, study assessments planned in the protocol will be limited to the ones possible remotely, denoted with an asterisk (\*) in Table 2, Table 3, Section 5.2.2, Section 5.2.3 and Section 5.2.4; of note no study assessments should be performed remotely for the Screening, Baseline and EOS/EWD visits. Completion of questionnaires on the subjects' own device will be performed provided that the site staff can access the ePRO system to record the visit date.

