#### 5.2.1.1 Screening – Visit 1 - Day -14 (-14 days/ +3 days)

The Screening Visit (Visit 1) will take place on Day -14 of the study. The visit window will be from Day -28 to Day -11.

The following assessments will be performed:

- Eligibility check (inclusion/exclusion criteria)
- Demographic data (year of birth, age, sex, ethnicity, and race)
- Medical history, including significant ongoing medical history, surgical history and vulvodynia history
- Vital signs (supine or sitting blood pressure and heart rate)
- Body height and weight
- Physical examination
- Blood sampling (nonfasting) for haematology, biochemistry, putative antibodies and FSH

- Urine pregnancy test
- Urine test for illicit drugs
- Vaginal culture/polymerase chain reaction for yeast, parasitic and bacterial infections
- PCS
- mFSFI (pain to be recorded at the visit, and 1 week prior to the Baseline Visit; other domains to be recorded only at the visit)
- Relationship/partner status (to be recorded at the visit and then weekly during the screening period)
- mVPAQ (pain and life interference to be recorded at the visit, and 1 week prior to the Baseline Visit; other subscales to be recorded only at the visit)
- Intercourse details (to be recorded daily during the screening period)
- Dilator size 6 insertion details (to be recorded weekly during the screening period)
- PGI-S (to be recorded at the visit, and 1 week prior to the Baseline Visit)
- Q-tip test
- Dilator test
- Record:
  - Prior and concomitant medications/therapies (including pain rescue medication) administered within 28 days before the Screening Visit
  - Prior pelvic floor physical therapy or sex therapy received in the past 2 years prior to the planned Baseline
  - Treatment for anterior vestibular pain
  - Prior treatment with any BTX within the last 1 year
  - Prior and concomitant nondrug therapies and surgical procedures administered within 28 days before the Screening Visit
  - Use of any experimental new drug or device within past 4 weeks prior to the planned Baseline.
- Collection of AEs (since the signature of the informed consent)
- Instructions on patient diary completion.

Following confirmation of eligibility of the subject for the study and confirmation that the recruitment is still open in the cohort/group, subjects will be randomised and allocated to one of the dosing groups specified in Section 3.7.2.

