### **5.2.2 Procedures During Double-Blind Period – Treatment Cycle 1 (Stage 1 + Stage 2)**

#### **5.2.2.1 Baseline Visit (Day 1)**

The following procedures will be performed prior to the administration of study treatment:

- Eligibility check (inclusion/exclusion criteria)
- PGI-S (to be recorded 1 week prior to the visit and at the visit)
- mFSFI (pain to be recorded 1 week prior to the visit and at the visit; other domains to be recorded only at the visit)
- Relationship/partner status (to be recorded weekly from 2 weeks prior to the visit and at the visit)
- mVPAQ (pain and life interference to be recorded 1 week prior to the visit and at the visit; other subscales to be recorded only at the visit)
- PHQ-9
- SF-36
- Intercourse details (to be recorded daily from 2 weeks prior to the visit)
- Dilator size 6 insertion details (to be recorded weekly from 2 weeks preceding the visit; assessment on the day of the visit should be avoided)
- Dilator test
- Measurement of pelvic floor muscle pressure (in all subjects in Stage 1 up to 400 U and in a subset of subjects in Stage 2 (i.e. in subjects who have never had a vaginal delivery (including attempted vaginal delivery), and at study sites that were provided a perineometer))
- Review of AEs
- New or changed concomitant medications/nondrug therapies
- Randomisation.

Once these procedures have been performed, the study treatment will be injected as described in Section [6.2.2](#).

Following injection, subjects will be observed at the study centre for at least 30 minutes.

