### **5.2.3 Procedures During Open-Label Period – Treatment Cycles 2 to 4 (Stage 1 + Stage 2)**

#### *5.2.3.1 Day 1 Visit (Treatment Visit)*

The following procedures will be performed prior to the administration of study treatment:

- Urine pregnancy test
- Urine test for illicit drugs
- Review of AEs (only if the visit is not on the same day as the last visit of the previous cycle)
- New or changed concomitant medications/nondrug therapies (only if Day 1 is not on the same day as the last visit of the previous cycle).

If the visit occurs more than 2 weeks after the last visit of the previous treatment cycle, the following procedures will be done:

- PGI-S (to be recorded 1 week prior to the visit and at the visit)
- PGI-C (to be recorded 1 week prior to the visit and at the visit)
- Relationship/partner status (to be recorded weekly from 2 weeks prior to the visit and at the visit)
- Intercourse details (to be recorded daily from 2 weeks prior to the visit)
- Dilator size 6 insertion details (to be recorded weekly from 2 weeks preceding the visit; assessment on the day of the visit should be avoided)
- Dilator test
- CGI.

Once these procedures have been performed, the study treatment will be injected as described in Section 6.2.2.

Following injection, subjects will be observed at the study centre for at least 30 minutes.

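### The first injection rests on a pregnancy test 11 to 28 days old, while every open-label injection needs a negative test that day; repeat the urine test at Baseline

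*Protocol*

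**What the plan says.** **Before the first injection.** Inclusion criterion 5 (Protocol section 4.1) reads "Have a negative pregnancy test at screening". Section 5.2.1.1 sets the timing of that visit: "The visit window will be from Day -28 to Day -11". Section 5.2.2.1 introduces the Baseline list with "The following procedures will be performed prior to the administration of study treatment". The list includes an eligibility check, the dilator test and randomisation, but no pregnancy test. Table 2 agrees: the urine pregnancy test is marked at Screening and at End of Cycle 1 (or end of study or early withdrawal), not at Baseline. Section 5.2 supplies the bridging rule: "For assessments done at the Screening Visit, but not repeated at the Baseline Visit, the Screening values will be considered as Baseline".

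**Before each open-label injection.** Section 3.7.3 makes "Negative urine pregnancy test" one of the conditions that must all be met for retreatment. Section 5.2.3.1 lists "Urine pregnancy test" among the procedures done on Day 1 before dosing. Footnote c of Table 3 gives the only waiver: "Not to be performed if already done on the same day".

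**The exclusion the test serves.** Exclusion criterion 19 (section 4.2) bars a "Female subject who is pregnant or planning to become pregnant during the study".

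**The concern.** All subjects are premenopausal. Eligibility is rechecked on Day 1, and that check covers exclusion 19, but no current test result supports it. Two kinds of subject could pass the check and be injected: a woman who conceives between Screening and Day 1, and a woman whose pregnancy was too early to detect at Screening. A site following the protocol exactly could therefore inject someone the protocol means to exclude.

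The error could also go unnoticed for some time. After Screening, the next scheduled pregnancy test is at End of Cycle 1, at Week 12 at the earliest and Week 36 for a subject who is never retreated, unless she withdraws early. Section 8.2.3 withdraws any subject who becomes pregnant and section 8.1.7 bars further study drug, so preventing the first exposure serves an aim the protocol already has.

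This is a matter of subject safety. It does not touch the endpoints, the error rates or the sample size.

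**Working it through.** **1. Reproduce the screening window.** The Screening Visit is nominally Day -14, with a window of -14/+3 days (section 5.2.1.1).
- Earliest: -14 - 14 = Day -28.
- Latest: -14 + 3 = Day -11.

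Both match the stated window.

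**2. Age of the test at injection.** The SAP (section 3.11, item 6) states that there is no Day 0, so Day -k lies k days before Day 1. The first injection is on Day 1 (section 3.1.1).

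| Injection | Age of last scheduled test |
|---|---|
| Cycle 1, screened on Day -11 | 11 days |
| Cycle 1, screened on Day -14 (nominal) | 14 days |
| Cycle 1, screened on Day -28 | 28 days |
| Cycles 2 to 4 | 0 days |

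**3. Chance of conceiving in the gap.** Inclusion 6 defines highly effective contraception as a failure rate below 1% per year, so r = 1% is used as the ceiling. With a gap of g days, the risk per subject is 1 - (1 - r)^(g/365.25).
- g = 11: 1 - 0.99^(11/365.25) = 0.0303%
- g = 14: 1 - 0.99^(14/365.25) = 0.0385%
- g = 28: 1 - 0.99^(28/365.25) = 0.0770%

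**4. Expected pregnancies.** The planned total is 118 in Stage 1 plus 63 in Stage 2 = 181. Cohorts 1 to 6, the only ones covered by the final analysis (SAP section 1.3.5), were planned at 10 + 10 + 10 + 8 + 10 + 10 = 58.

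| Gap | Per subject | In 181 | In 58 |
|---|---|---|---|
| 11 days | 0.0303% | 0.055 | 0.018 |
| 14 days | 0.0385% | 0.070 | 0.022 |
| 28 days | 0.0770% | 0.139 | 0.045 |

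**5. Sensitivity to the contraceptive method.** Inclusion 6 also lets the investigator accept condom plus spermicide, and the documents give no failure rate for it. As an assumed upper case, take 5% per year for every subject and the longest gap: 1 - 0.95^(28/365.25) = 0.392%. That gives 0.392% × 181 = 0.71 and 0.392% × 58 = 0.23.

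**6. What the figures leave out.** They count conceptions inside the gap. Pregnancies that began before Screening and were undetectable then are not counted, and the documents give no basis for a rate. Nor are the figures the number of injections a Day 1 test would prevent, because a very recent conception could still test negative on Day 1.

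**The case against.** The strongest reply is that the protocol is internally consistent and the comparison with retreatment is not like for like. Section 5.2 openly treats an unrepeated screening value as the Baseline value. Retreatment comes at least 12 weeks (84 days) after the previous injection. Without its own test, the last result at cycle 2 would be at least 11 + 84 = 95 days old, against 11 to 28 days at the first injection. The illicit-drug test follows the same pattern: done at Screening, absent from the Baseline list, and required to be negative for retreatment. On this reading the structure is deliberate.

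Mitigation is also real. Contraception is required, eligibility is rechecked on Day 1, intercourse is recorded daily during screening, and subjects must report a pregnancy at once (section 8.1.7). Section 1.3.1 reports that the drug was not teratogenic in rats or rabbits. Some first injections are placebo. At the nominal 14 days and 1% per year, 0.022 expected pregnancies in 58 subjects is about one in 45 trials of that size (1/0.022). The 0.71 figure needs an assumed rate for everyone, the longest gap for everyone, and a Stage 2 that never ran.

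Most of this stands as evidence that the risk is small. It does not supply a current result for the Day 1 check. Contraception is framed as willingness from the beginning of the study, so it does not cover a conception shortly before Screening. Diary entries show exposure, not pregnancy, and self-report works only once the woman knows. The protocol also ties other criteria expressly to Baseline (inclusion 10a, exclusions 2b and 7a), so dating this one there would fit its own practice. The longer interval explains why retreatment needs a test. It does not explain why 11 to 28 days is short enough to do without one.

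**Conclusion.** The concern holds. Before the first injection the only scheduled pregnancy test is 11 to 28 days old (nominally 14); before every open-label injection it is 0 days old. This is a weak point in the design, not a contradiction between rules.

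At the 1% per year ceiling the exposure is 0.05 to 0.14 expected conceptions in 181 planned subjects, or 0.02 to 0.04 in the 58 planned for Cohorts 1 to 6. Under the assumed 5% rate with a 28-day gap it is 0.71 and 0.23. These figures rest on planned numbers and on a constant failure rate over the gap, and they exclude pregnancies missed at Screening.

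The case for change rests on the low cost of the remedy and on the sponsor's own injection-day standard, not on a large expected count. The sponsor closed the study before Stage 2, so the correction cannot alter conduct here; it applies to any reuse of the design.

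**What to change.** Add the urine pregnancy test to the Baseline (V2) column of Table 2 and to the list in section 5.2.2.1, with a negative result required before randomisation and injection. Amend inclusion 5, in section 4.1 and in the synopsis, to require a negative test at Screening and again at Baseline.

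The cost is one urine test per subject. Baseline is always an on-site visit, since section 5.2 rules out remote assessments there, and section 8.2 already has urine samples analysed at the site. Blinding, endpoints and sample size are unaffected. The test age at first injection falls from 11 to 28 days to 0 days. Because a very early conception can still be missed on Day 1, the gap is narrowed, not closed.

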#### 4.2 Exclusion Criteria

Subjects will not be included in the study if they meet any of the following exclusion criteria:

- (1a) Have provoked pain on a Q-tip test at the anterior vestibule (anywhere between 9 and 3 o'clock or more anteriorly) at the Screening Visit.
- (2b) Able to tolerate the 6th (diameter 1½ inches) dilator size (i.e. agree to the next successive dilator size to be tested for pain response) at the Baseline Visit (i.e. at least one of the two largest sized dilators (#7 and/or 8) is tested).
- (3a) Any non-provoked (i.e. spontaneous) vulvar pain in the past 6 months prior to the Screening Visit. Note: pain provoked by any vestibular pressure (including but not limited to sitting, bicycling or tight clothing) is considered provoked pain.
- (4a) Deep pain during intercourse in the past 6 months prior to the Screening Visit.
- (5a) Score of 4 or 5 on any of the 3 pain questions (questions #17, 18 or 19) of the mFSFI questionnaire.
- (6) *Criterion 6 is removed by previous protocol amendment.*
- (7a) Significant depressive disorder, e.g. having a score  $\geq 20/27$  on the Patient Health Questionnaire (PHQ-9) scale at the Baseline Visit.
- (8b) Genitourinary or gastrointestinal conditions/history including:
  - Skin disease at the vestibule such as lichen sclerosus, lichen planus, vaginal or vulvar atrophy, desquamative inflammatory vaginitis and allergic vulvitis.
  - Severe endometriosis (severe defined as requiring regular medications to manage the endometriosis symptoms).
  - Severe bladder and bowel symptoms e.g. diagnosed interstitial cystitis/Bladder Pain Syndrome, severe urinary incontinence, faecal incontinence, inflammatory bowel disease.
  - Genitourinary or rectal cancer.
  - Congenital urogenital abnormalities (e.g. vaginal septa, imperforate hymen, urethral diverticulum).
  - Pain in urethra (diagnosis based on subject's interview and physical examination).
  - Symptomatic urogenital prolapse at physical examination.
  - History of traumatic or post radiotherapy vulvar lesions.
  - Pudendal neuralgia
  - Other conditions that in accordance to the investigator's judgement may interfere with treatment or impact the study outcome.
- (9) Previous surgery/conditions including:
  - Hysterectomy
  - Vestibulectomy
  - Urologic surgery
  - Perianal surgery
  - Genital trauma or mutilation/cutting
  - Other surgery/conditions that according to the investigator's judgement may impact the study outcome

(10) Vaginal infections (bacterial vaginosis, presence of candidiasis or trichomoniasis) at Screening Visit.

(11) Current infection at the injection site(s).

(12) Unable to receive intramuscular injections.

(13) History of hypersensitivity to Dysport or drugs with a similar structure or any excipient used in the formulation.

(14) Clinically significant history of alcohol/drug abuse the last 24 weeks prior to screening or clinically significant alcohol/drug dependence within 2 years prior to screening. Exceptions include caffeine or nicotine abuse/dependence.

(15a) Positive urine test for illicit drugs (drugs of abuse) at screening. In the event a subject tests positive for cannabinoids (tetrahydrocannabinol), the investigator will evaluate the subject's ability to abstain from cannabis during the study. If in the investigator's clinical judgement, the subject will abstain, the subject may be enrolled after consultation with the Medical Monitor. Note: at the discretion of the investigator, positive drug screens for prescribed medications will not be considered exclusionary.

(16c) Has received any of the following:

- Pelvic floor physical therapy initiated, stopped or modified (frequency or type of physical therapy) during the last 12 weeks prior to Baseline (physical therapy includes but is not limited to: internal/external myofascial release by physiotherapist, biofeedback, home pelvic floor exercises, self-taught exercises, use of vaginal dilators, etc.).
- Sex therapy in the past 6 weeks prior to Baseline.
- Previous treatment with any BTX for any indication within the last 1 year.
- Treatment for vestibular pain, with hormonal creams, in the last 1 week prior to Screening unless continued at the same dosing regimen throughout the study.
- Currently receiving treatment for stress or urge urinary incontinence.
- Treatment with any of the following drugs that could affect neuromuscular function: curare-like nondepolarising agents, lincosamides, polymyxins, anticholinesterases, aminoglycoside antibiotics (topical use is permitted except at the vulvar vestibular region), tizanidine and baclofen, within the last 4 weeks prior to Baseline or during the study.
- Injections of steroids in the vulva within the last 4 weeks prior to the Screening Visit or planned use during the study.
- Treatment with an investigational drug within the last 4 weeks prior to Baseline or scheduled treatment with such a drug during the study period.
- Is likely to require treatment during the study with drugs that are not permitted by the study protocol.

(17) Any mental condition rendering the subject unable to understand the nature, scope and possible consequences of the study, and/or evidence of an uncooperative attitude, as judged by the investigator.

(18) Abnormal baseline findings, any other medical condition(s) or laboratory findings that, in the opinion of the investigator, might jeopardise the subject's safety or compromise compliance with the objectives and/or procedures of this protocol or preclude the administration of BTX.

(19) Female subject who is pregnant or planning to become pregnant during the study or, is currently lactating (breastfeeding).

